6.5. Pharmacokinetic and Pharmacodynamic Analysis Set

All participants who receive at least 1 dose of ravulizumab and who have evaluable PK or pharmacodynamic (PD) data will be included in the PK/PD Analysis Set. PK and PD analyses will be performed on the PK/PD Analysis Set.

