## 6. STUDY INTERVENTION

Study intervention is defined as any investigational intervention(s), marketed product(s), placebo, or medical device(s) intended to be administered to a study participant according to the study protocol.

For this study, the study intervention will include the administration of study drug (ravulizumab or placebo) in addition to BSC.

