## **8.7. Pharmacokinetics and Pharmacodynamics**

- Blood samples for determination of serum drug concentrations and PD assessments (free and total C5) will be collected before and after administration of study drug at the time points specified in the Schedule of Activities (Section 1.3).
- Instructions for the collection and handling of biological samples, including blood volume requirements, are provided in the Laboratory Manual. The actual date and time (24-hour clock time) of each sample will be recorded.
- The Day 1 baseline PK and PD blood samples will be collected at predose, within 90 minutes before administering study drug (Section 1.3). The predose blood sample may be drawn through the venous access created for the dose infusion, prior to administration of the dose.
- All subsequent predose samples will be collected within 0.5 hours prior to the start of infusion. In order to minimize needle sticks to the participant, the predose sample

may be drawn through the venous access created for the dose infusion, prior to administration of the dose.

- Postdose PK and PD blood samples will be collected within 0.5 hours after completion of the study drug infusion. The postdose blood samples will be drawn from the participant's opposite, noninfused arm.
- For indicated visits not falling on dosing days, samples may be collected at any time that visit day.
- In the event of an unscheduled visit, PK and PD blood sample will be collected as soon as possible.

Study drug concentration information that may/would unblind the study will not be reported to investigative sites or blinded personnel until the study has been unblinded.

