### 9.3. Populations for Analyses

The population sets used for analysis are defined in the following:

Population	Description
Intent to Treat	All randomized participants
Modified Intent to Treat (mITT)	All randomized participants, excluding participants who enroll prior to availability of ST-HUS and ADAMTS13 central laboratory results and are subsequently found to be ineligible after randomization
Safety Set	All participants who receive at least 1 dose of study drug. Participants will be analyzed according to the study drug they actually received for reporting exposure and safety data
Pharmacokinetic/Pharmacodynamic (PK/PD) Analysis Set	All participants who receive at least 1 dose of study drug and who have evaluable PK/PD data
Per Protocol (PP) Set	To be defined in the Statistical Analysis Plan

Abbreviations: ADAMTS13 = a disintegrin and metalloproteinase with a thrombospondin type 1 motif, member 13; ST-HUS = Shiga toxin-related hemolytic uremic syndrome

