7.6. Pharmacokinetic and Pharmacodynamic Analyses

Individual PK/PD data will be collected for all participants. PK/PD analyses will be performed on the PK/PD Analysis Set.

Serum ravulizumab concentration will be summarized over time with descriptive statistics, including the number of observations, arithmetic mean, SD, median, minimum, maximum, coefficient of variation, geometric mean, and geometric coefficient of variation.

The PD effects of ravulizumab will be evaluated by assessing the observed values, changes and percentage changes from Baseline in serum free and total C5 concentrations over time, as appropriate. Summaries will present descriptive statistics at each sampling time, as appropriate.

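### SAP 6.5 narrows the PK/PD Analysis Set to ravulizumab recipients without declaring the change, so placebo free and total C5 data drop out of the PD summaries

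*SAP*

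**What the plan says.** The two documents define the same analysis set differently.

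- Protocol 9.3 includes "All participants who receive at least 1 dose of study drug and who have evaluable PK/PD data". Section 6 of the protocol says that "the study intervention will include the administration of study drug (ravulizumab or placebo) in addition to BSC", so a dosed placebo participant with evaluable data belongs to the set.
- SAP 6.5 includes "All participants who receive at least 1 dose of ravulizumab and who have evaluable PK or pharmacodynamic (PD) data" and adds that "PK and PD analyses will be performed on the PK/PD Analysis Set".
- SAP 7.6 states that "Individual PK/PD data will be collected for all participants", and then places the analyses on the restricted set. The PD outputs are observed values, changes and percentage changes from baseline in free and total C5.
- Protocol 8.7 makes no distinction by arm: "PD assessments (free and total C5) will be collected before and after administration of study drug", and study drug covers both arms.
- SAP 4.2 and 4.3 record several departures, among them the addition of the mITT Set, the removal of the Enrolled Set and the revised Per-Protocol Set. The PK/PD set is not mentioned.

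**The concern.** Free and total C5 (absolute value, change and percentage change from baseline) are endpoints in Protocol Table 4. They are the direct measure of whether the dosing regimen inhibits terminal complement in this population as the dose rationale in Protocol 4.3 expects. The trial has a randomized placebo arm with the same sampling schedule, yet the SAP as written leaves that arm out of the C5 tables.

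What remains is a before-after summary in one arm. Participants enter acutely ill, their trigger may be treated as part of best supportive care (Protocol 6.5), and plasma exchange or infusion is prohibited only from randomization onward during the Treatment Period (Protocol 6.6.2). C5 could therefore change after Day 1 for reasons other than the drug. A concurrent placebo column is the simplest way for a reader to judge that.

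Because the change is undeclared, a reader of the study report would also have reason to assume that the protocol's set had been used.

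**Working it through.** No sample size, power or alpha figure is involved. The check is a comparison of text followed by a count of samples.

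**Step 1: who is in each set.**

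| Participant | Protocol 9.3 | SAP 6.5 |
|---|---|---|
| At least one dose of ravulizumab, evaluable data | In | In |
| Placebo only, evaluable data | In | Out |
| Randomized to placebo, known to have received ravulizumab | In | In |

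The difference is exactly the participants who received only placebo.

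**Step 2: does the difference reach the C5 tables?** Yes. SAP 6.5 and 7.6 both put the PD analyses on this set, and no other section of the SAP provides a placebo C5 summary. SAP 7.1 asks for display by treatment group where that applies, but for C5 only one group is left. The immunogenicity results are handled differently: SAP 7.7.3.4 summarises antidrug antibodies by treatment group, on the Safety Set (SAP 7.7).

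**Step 3: samples scheduled per participant** (Protocol Tables 1 and 2).

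- Predose on Days 1, 15, 71 and 127, plus Day 183: 5
- Postdose on Days 1, 15, 71 and 127: 4
- Follow-up at Weeks 34 and 52: 2

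Treatment Period: 5 + 4 = 9. Whole study: 9 + 2 = 11.

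**Step 4: samples left out.** SAP Section 4 gives 16 enrolled and 1:1 randomization but not the split by arm. Assume 16 / 2 = 8 on placebo.

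- Treatment Period only: 8 × 9 = 72
- With both follow-up samples: 8 × 11 = 88

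If the split were 7 or 9 on placebo, the counts would be 63 or 81 (Treatment Period) and 77 or 99 (whole study). For a given split these are ceilings, since they assume that every scheduled sample was taken. Missed visits and early discontinuation lower them. The Week 34 and Week 52 samples are doubtful for later enrollees, because SAP Section 4 reports a decision to end the study once the last participant on treatment completes 26 weeks.

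**The case against.** The strongest reply is that little that was planned is lost. Protocol 9.4.3 evaluates the PD effects of ravulizumab through descriptive statistics on values and changes from baseline, with no between-arm contrast. SAP 4.2 removes all inferential treatment comparisons. A ravulizumab-only set is natural for serum drug concentration. All of this stands, and it limits the loss to a descriptive placebo column. It does not explain why the set was narrowed for C5, or why the change is undeclared. Protocol 9.4, like SAP 7.1, also calls for summaries by treatment group where applicable.

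A reader might infer more than the documents support:

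- **That a formal placebo comparison of C5 has been dropped.** None was planned in Protocol 9.4.3.
- **That a safeguard against kit or dosing errors has been removed.** Neither document describes a check for drug or suppressed C5 in placebo participants. A participant known to have received ravulizumab in error would still enter the SAP set, and dosing is supervised and recorded (Protocol 6.4).
- **That recovery or clearance of donor plasma materially biases the total C5 results.** The mechanism is plausible, but the documents give no figure for its size. If free C5 suppression is as complete as the protocol expects, it will be visible without a control.
- **That the planned trial would have lost 50 × 11 = 550 samples.** This SAP version governs the terminated 16-participant study, not the planned one.

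**Conclusion.** Wrong as written, minor severity. The SAP contradicts the protocol's definition of the PK/PD set, does not declare the change, and so excludes the C5 data of placebo-only participants from a protocol endpoint. What is lost is a descriptive control arm: at most 72 samples in the Treatment Period, or 88 if both follow-up samples exist for every placebo participant. Both figures rest on an assumed 8/8 split and complete sampling. The primary endpoint, the efficacy analyses and the safety analyses are unaffected. The point is still worth correcting: with inferential testing dropped and 16 participants enrolled, side-by-side description is what the trial can still offer on C5.

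**What to change.** In SAP 6.5, restore the protocol's definition for PD: at least one dose of study drug and evaluable PD data. In SAP 7.6, state that free and total C5 (observed value, change and percentage change) will be summarised descriptively by treatment group at each sampling time. Keep the serum ravulizumab concentration summaries to ravulizumab recipients. Optionally, list any measurable concentration in a placebo participant.

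If the restriction was intended, SAP 4.2 should declare and justify it. That would settle the inconsistency but would still leave C5 without a control column.

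The cost is a sentence or so in each section, plus assays of any placebo samples not yet run. No additional sampling is needed, since the protocol already schedules it for all participants.

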7. STATISTICAL ANALYSIS

7.1. General

All analyses will be performed using Statistical Analysis Software[®] (SAS[®]) Version 9.4 or higher (SAS Institute Inc., Cary, NC, USA) or other validated statistical software.

Summary statistics will be computed and displayed by treatment group, and by visit, where applicable. Descriptive statistics for continuous variables will include the number of participants, mean, standard deviation (SD), minimum, median, and maximum. For categorical variables, frequencies, and percentages will be presented.

7.1.1. Handling Missing Data

For binary endpoints, a nonresponder imputation (NRI) method will be used by categorizing any participants who have a missing value for categorical variables at a specific visit as a nonresponder for that visit. In addition, participants who have the following intercurrent events will be assigned as nonresponders, regardless of whether any response is observed after these intercurrent events: premature discontinuation of the study treatment or initiation of disallowed therapy or medicine, before observing the response for an endpoint in analysis.

For time-to-event endpoints (time to complete TMA response, time to response for each individual TMA parameter), missing data and data after intercurrent events of premature discontinuation of study treatment or initiation of disallowed therapy or medicine will be censored.

For the continuous secondary endpoint, no missing data handling will be performed. Summary statistics will be provided using observed data.

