This was a Phase 3, randomized, double-blind, placebo-controlled study of ravulizumab in addition to best supportive care (BSC) in adult participants (\geq 18 years of age) with thrombotic microangiopathy (TMA) following a defined trigger. All participants had severe acute kidney injury and a diagnosis of TMA based on protocol-defined criteria (ie, thrombocytopenia, microangiopathic hemolytic anemia, and elevated lactate dehydrogenase [LDH]), which was associated with at least 1 trigger, such as autoimmune, infection, solid organ transplant, drugs, or malignant hypertension, occurring \leq 14 days prior to randomization.

The study consisted of an up to 2-week Screening Period, a 26-week randomized Treatment Period, and a 26-week Post-treatment Follow-up Period. Thus, the total treatment duration was 26 weeks, and the total study duration was up to 54 weeks.

Participants were screened for eligibility for up to 2 weeks during the Screening Period. Approximately 100 adult participants were planned to be randomized in a 1:1 ratio to receive either ravulizumab or placebo. Randomization was stratified by baseline dialysis status and by primary trigger type.

During the 26-week Treatment Period, all participants received a weight-based loading dose of ravulizumab or placebo on Day 1, followed by weight-based maintenance doses of ravulizumab or placebo on Day 15 and then once every 8 weeks (q8w) thereafter. All participants received BSC throughout the study.

During the 26-week Post-treatment Follow-up Period, participants continued to receive BSC at the discretion of the Investigator and will be monitored for safety, TMA response, and clinical events of interest.

The end of the study was defined as the last participant's last visit in the Post-treatment Follow-up Period.

Enrollment in the study was closed, and the decision to terminate the study when the last participant in treatment has completed the 26-week Treatment Period was made on 24 Oct 2022.

Disclosure Statement: This was a parallel group treatment study with 2 arms that was participant, Investigator, and outcomes assessor blinded.

Number of Participants: It was planned that approximately 100 participants would be enrolled in the study. A total of 16 participants were enrolled in the study.

Intervention Groups and Duration:

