4.1. Planned Analyses

A primary endpoint analysis to assess sample size re-estimation was planned to be conducted at the interim time point, when 50% of the 100 planned participants have been followed for 26 weeks from randomization or withdrawn from the initial 26 weeks of the study and have been assessed for the primary endpoint. The primary analysis was planned to be conducted after all participants complete Week 26 or withdraw from the study prior to Week 26. Analyses will be performed on data for the 26-week randomized Treatment Period. The final study analysis was planned to be conducted at the end of the study.

Due to the early termination of the study, the planned interim analysis for sample size re-estimation and the planned primary analysis will not be conducted, and the final study analysis will be performed after the last participant in the study has completed the 26-week Treatment Period.

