5.2. Secondary Endpoints

The following is a list of secondary efficacy endpoints. Due to early termination of the study, there are no longer any "key secondary endpoints" with multiplicity adjustment.

- 1. Time to complete TMA response (measured in days from Day 1 to the first day that the participant satisfies the criteria for complete TMA response) during the 26-week randomized Treatment Period.
 - TMA response occurs on the first day when all components of TMA response are met simultaneously, with each component meeting the requirement at 2 separate assessments obtained at least 24 hours apart, and any measurement in between.
- 2. Achievement of hematologic response at Week 26.
- 3. Change from Baseline in eGFR at Week 26.
- 4. On dialysis at Week 26.
- 5. Time to response for each TMA parameter (Table 2) during the 26-week randomized Treatment Period
 - Hematologic response
 - Renal response
- 6. Achievement of individual component of complete TMA response at all scheduled assessments
 - Hematologic response
 - Renal response
 - At least one of the TMA parameters
- 7. Changes from Baseline in hematologic response parameters at all scheduled assessments
 - Platelets
 - LDH
 - Hemoglobin
- 8. Increase in hemoglobin at Week 26 of
 - $\geq 2 \text{ g/dL}$
 - $\geq 1 \text{ g/dL}$
- 9. Change in kidney function
 - Change from Baseline in eGFR at all scheduled assessments
 - Change from Baseline in dialysis requirement at Week 26 and Week 52
 - Duration of dialysis (for participants who had dialysis within the 26-week randomized Treatment Period or within the study)

- 10. Complete TMA response at Week 52 among participants who achieved complete TMA response during the 26-week randomized Treatment Period
- 11. Loss of TMA response during the 26-week randomized Treatment Period (for participants who achieved complete TMA response during the 26-week randomized Treatment Period)
- 12. TMA relapse during the Post-Treatment Follow-up Period (for participants who achieved complete TMA response during the 26-week randomized Treatment Period)
- 13. Change in patient-reported outcomes as measured by Functional Assessment of Chronic Illness Therapy-Fatigue (FACIT-Fatigue) at all scheduled assessments

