7.3.2. Secondary Analyses

All secondary analyses will be performed on the mITT Set.

For time-to-event endpoints, Kaplan-Meier cumulative distribution curves will be generated for each treatment group. A corresponding summary table will present by treatment group the cumulative distribution function estimate, the number of participants at risk, the number of participants responding, and the number of participants censored at each post-Baseline time point. The table will also present the first quartile, median, and third quartile, along with the corresponding 2-sided 95% CI, of time to response.

The binary additional secondary endpoints will be summarized by randomized treatment group by calculating the point estimate and 2-sided 95% CI for the response rate, based on exact confidence limits using the Clopper-Pearson method (Clopper, 1934). NRI will be used to handle missing data.

For continuous additional secondary endpoints, descriptive statistics, including the number of participants, mean, SD, minimum, median, and maximum, will be provided based on observed data.

For participants who require dialysis, change from Baseline in dialysis requirements will be summarized. An analysis will present the number and proportion of participants who require dialysis over time. A 2-sided 95% CI for the proportion will be provided. A participant will be considered as not requiring dialysis at a specific post-Baseline time point if they have been dialysis free for at least 14 days prior to that time point.

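### Non-responder imputation has no exception for follow-up cut short by sponsor termination, so a treatment-period responder may be scored as a Week 52 failure (minor)

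*SAP*

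**What the plan says.** **Missing-data rule.** SAP 7.1.1 applies NRI to binary endpoints by "categorizing any participants who have a missing value for categorical variables at a specific visit as a nonresponder for that visit". It adds two intercurrent events that also give nonresponse: stopping study treatment early and starting a disallowed therapy. Sponsor termination is not mentioned. SAP 7.3.2 says again, for binary secondary endpoints, that "NRI will be used to handle missing data". For the continuous secondary endpoint, 7.1.1 says that "no missing data handling will be performed" and that summaries use observed data. Missing time-to-event data are censored.

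**Termination.** SAP Section 4 states that the decision to "terminate the study when the last participant in treatment has completed the 26-week Treatment Period was made on 24 Oct 2022", and that "A total of 16 participants were enrolled in the study". Section 4.1 drops the interim and primary analyses and says that "the final study analysis will be performed after the last participant in the study has completed the 26-week Treatment Period".

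**Endpoint kept.** Item 10 of SAP 5.2 is "Complete TMA response at Week 52 among participants who achieved complete TMA response during the 26-week randomized Treatment Period".

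**The concern.** The denominator of endpoint 10 is fixed at Week 26, but its numerator needs a Week 52 value. With closure tied to the last Week 26 visit, participants who enrolled late cannot supply one. Under the written rule, a late-enrolled responder is then reported as not in response at Week 52, although nobody observed a loss of response. What decides this is enrolment date, not disease.

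The SAP was revised for the termination: tests, estimands and the interim analysis were removed. The NRI rule was carried through without an exception. The result is uneven. A truncated responder's Week 52 FACIT-Fatigue score is simply left out of the summary, and MACE rates to Day 365 (SAP 7.7.2.4) are expressed per patient-year of follow-up, but the Week 52 response becomes a failure. At stake is the one rate in the SAP that describes whether response lasts after treatment stops, together with its Clopper-Pearson interval.

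**Working it through.** **The plan's own figure.** SAP 9.2 gives about 90% power for 35% versus 70% with 50 per arm, a two-sided Fisher's exact test at 0.05 and 10% dropout. Exact enumeration gives 88.3% at 45 per arm (50 × 0.9) and 93.1% at 50 per arm, so the figure reproduces once dropout is taken off. The concern does not rest on it; only the design rates are borrowed below.

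**Inputs.** 16 enrolled (SAP 4); 1:1 randomization (SAP 4); design rates 35% and 70% (SAP 9.2); Week 26 at Day 183 and Week 52 at Day 365 ± 7 (Protocol Tables 1 and 2); laboratory draws in follow-up scheduled only at Week 52 (Protocol Table 2). Assumption: 8 per arm, since the actual split is not given.

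**Step 1: who is truncated.** Suppose the last participant to finish is seen on Day 183 and the study closes that day. Someone randomized *d* days earlier is then at Day 183 + *d*. Whether that person has a Week 52 value depends on how follow-up visits are assigned:

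- *Nominal label.* Protocol Table 2 names the visit W52/EOS. A closing follow-up sample could count whatever its day.
- *Midpoint windows of SAP 9.3.6, if they extend to follow-up.* 365 − 183 = 182 days, an even number, so the middle day 183 + 91 = 274 belongs to the later window. A sample counts from Day 274, so *d* ≥ 91.
- *A true Week 52 visit.* 365 − 7 = 358, so *d* ≥ 175 at the early edge of the window and *d* ≥ 182 for Day 365.

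The documents do not choose among these. On each of them the last participant to finish (*d* = 0) has no post-treatment follow-up, so at least one participant is truncated. Whether that person was a responder is not stated.

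**Step 2: size per truncated responder.** In one arm let R be the treatment-period responders, *k* those truncated, *h* those among the *k* who would still have been in response at Week 52, and *s* those observed in response at Week 52.

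- Rate as written: *s*/R
- Rate with full follow-up: (*s* + *h*)/R
- Understatement: *h*/R, at most *k*/R

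So one truncated responder costs at most 1/R, and costs nothing if response would have been lost anyway.

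**Step 3: illustration.** 8 × 0.35 = 2.8, so R ≈ 3; 8 × 0.70 = 5.6, so R ≈ 6. Assume every responder holds response to Week 52.

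| R | k | As written (95% CI) | Evaluable only (95% CI) | Loss |
|---|---|---|---|---|
| 3 | 1 | 2/3 = 66.7% (9.4–99.2) | 2/2 = 100% (15.8–100) | 33.3 points |
| 6 | 1 | 5/6 = 83.3% (35.9–99.6) | 5/5 = 100% (47.8–100) | 16.7 points |
| 6 | 3 | 3/6 = 50.0% (11.8–88.2) | 3/3 = 100% (29.2–100) | 50.0 points |

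**The case against.** The best case against rests on four points.

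*A closing visit may supply the value.* Protocol 7.2 asks for an EOS visit from those who withdraw during follow-up, Protocol 10.1.8 expects an EOS or ED visit before a site closes, and the visit carries the label W52/EOS. This stands in part: the affected group may be small. It does not help anyone with no follow-up visit, and the SAP does not say that such a sample counts as Week 52.

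*The analysis is descriptive.* True. SAP 4.2 removes all testing and SAP 5.2 removes the key secondary tier, so there is no type I error issue. This limits severity but does not make the reported rate right.

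*NRI is conservative.* That argument belongs to treatment comparisons, which have been dropped. Within an arm, NRI here only understates durability.

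*Disposition will show who left and why.* SAP 7.2.1 does this by arm for all randomized participants, but it leaves the endpoint 10 rate as it is.

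A reader might also infer stronger things that the documents do not support:

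- *A fixed cut-off, such as about 13 weeks before the last finisher.* This follows only if the midpoint windows apply after Week 26. SAP 9.3.6 gives its day count for the Treatment Period alone.
- *A single closing sample can never confirm response.* Protocol 3.2.1 requires a second assessment at least 24 hours after the first, but not that both fall in one visit window. The single scheduled follow-up draw also applies to everyone who does reach Day 365, so it is not an effect of termination.
- *The same damage to endpoint 6.* That item reads "Achievement of individual component of complete TMA response at all scheduled assessments", which could extend to Week 52. But Protocol 9.4.1.2.2 places the comparison of response rates within the 26-week Treatment Period, so the extension is possible, not established.

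**Conclusion.** The gap holds on the text. An explicit rule with no exception by reason, a retained Week 52 endpoint and a closure date tied to Week 26 together turn sponsor truncation into recorded failure. The bias in the endpoint 10 rate is downward or zero. It is at most 1/R per truncated responder: up to 33 points at R = 3 and 17 points at R = 6. Those two values rest on an assumed 8/8 split and the design response rates, and the full 1/R applies only if response would have been held. The number of truncated responders is not in the documents and may be zero.

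It would be wrong to read this as a flaw in the primary result or as a tilt towards one arm. Primary and Week 26 data are collected before closure, and truncation acts through enrolment date. With 16 participants a chance imbalance between arms could still colour a side-by-side reading. Severity: minor. Confidence is high in the textual gap and low in its realised size.

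**What to change.** In SAP 7.1.1 and 7.3.2:

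1. State that Week 52 binary values that could not be reached because the sponsor ended the study are administratively unobserved, not nonresponse.
2. Define the evaluable group by calendar date alone: follow-up could have reached the Week 52 visit before study closure. Outcome must play no part.
3. Report the numbers evaluable and truncated per arm beside the endpoint 10 rate.
4. Apply NRI only within the evaluable group, so that other missing Week 52 values are still counted as nonresponse.
5. Handle endpoint 6 in the same way if it is reported at Week 52.

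In SAP 9.3.6, state the rule that assigns follow-up samples to Week 52 (nominal label, midpoint window or protocol visit window), because the evaluable group depends on it. The response definition does not change.

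The cost is SAP wording and a changed denominator; no new data are needed. The downside is a smaller Week 52 denominator and a wider interval, and no estimate at all in an arm where every responder was truncated.
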